#### *Procedure of secondary outcomes*

Secondary complications and events are collected performing the same procedure of the primary outcomes. Questionnaires are provided online or on paper.

Physical tests are performed according to a standardized protocol. The 6MWT is executed on a flat 40-meter long indoor walking track. Patients are asked to walk for six minutes (without running) and are told that the distance is measured. If needed, patients are allowed to use an assistance device and take one or more rest breaks. Verbal encouragement (such as 'you're doing well') are given at the first, third and fifth minute. The time the patient is walking will be given at the second and fourth minute of the test. During the test, the operator walks close behind the patient and is attentive to any clinical manifestations that may influence the test's quality or require stopping prematurely. The walking distance during the test will be recorded. Heart rate and perceived exertion is conducted before and after the test.

Muscle strength is measured in the dominant hand and left leg (if arterial or venous of the hand/leg are used for the bypass of the surgery, the other hand/leg is used, resp. Jamar® Hand Hydraulic Dynamometer and Q Force). To get familiar with the grip and leg test, participants are requested to perform this test once. Patients start the STS test with their back against the chair and their arms folded across the chest. The researcher asks the patient to stand up and sit down 10 times as quickly as possible. Time is measured from the start to the end, which is when the buttocks touches the chair after the 5th repetition. To get familiar with the test patient have to do two repetitions before the test. For the test a standardized chair is used. The number of repetitions are counted when the patient is not able to complete 10 repetitions.

#### **7.4 Withdrawal of individual subjects**

Subjects can leave the study at any time for any reason if they wish to do so without any consequences. The reason to leave the study will be asked by the investigator; however the patient does not have to mention the reason. The investigator can decide to withdraw a subject from the study for urgent medical reasons.

##### **7.4.1 Specific criteria for withdrawal (if applicable)**

#### **7.5 Replacement of individual subjects after withdrawal**

Patients who withdraw from the study or who are unable to complete the study procedures are not replaced. A drop out of 20% is taken into consideration in the sample size calculation.

#### **7.6 Follow-up of subjects withdrawn from treatment**

After randomization, cardiac rehabilitation discontinuation for any reason does not constitute withdrawal from the study. Patients who prematurely withdraw from the study for any reason are asked to return all assessments as indicated in the study overview (Table 4). If the patient does not attend the study visits, follow-up should continue according to the specified schedule by online questionnaires or telephone, except in the case that the patient specifically refuses such follow-up.

### 7.7 Premature termination of the study

The study will be terminated prematurely when one of the CR programs is obviously ( $P<0.001$ ) worse or better than the other CR program (after interim analysis).

## 8. SAFETY REPORTING

### 8.1 Section 10 WMO event

In accordance to section 10, subsection 4, of the WMO, the investigator will suspend the study if there is sufficient ground that continuation of the study will jeopardise subject health or safety. The investigator will notify the accredited METC without undue delay of a temporary halt including the reason for such an action. The study will be suspended pending a further positive decision by the accredited METC. The investigator will take care that all subjects are kept informed.

### 8.2 AEs, SAEs and SUSARs

#### 8.2.1 Adverse events (AEs)

Adverse events are defined as any undesirable experience occurring to a subject during the study, whether or not considered related to the measurements of the study. All adverse events reported spontaneously by the subject or observed by the investigator or his staff will be recorded.

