### *Randomization*

Patients are randomized to two groups. One group will start a regular phase II CR program after surgery and are considered as the POST group. The other group will be randomized to a combined pre-and postoperative rehabilitation program (the PRE+POST CR program). The latter group is considered as the PRE+POST group. The PRE+POST group follows the CR program in the UMCG, location Beatrixoord. The POST group will receive the CR in the referred hospital. All hospitals provide a basic postoperative outpatient CR program, which is generally accepted care in the Dutch health care system. These CR programs are based on the multidisciplinary guidelines cardiac rehabilitation 2011 of the association of Dutch Cardiac Rehabilitation. The inclusion period is estimated to last 3.5 years, based on the power analyses (Section 3.4). The total study duration will therefore be 8.5 years (including follow-up of mortality up to five years). Patients are treated according to the intention to treat principles.

[figure not shown]

Figure 2: Research design of the randomized controlled trial. The phases of the CR programs and times of measurement are shown relative to the moment of surgery. T1 and T2 are preoperative measurements, T3, T4, T5 and T6 are postoperative and follow up measurements. Mortality is screened up to 5 years after surgery. H= hospital stay; OR = operation.

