An clinical relevant worsening is classified as minimal change according to Wyrwich et al., 2004 	
(Serious) Adverse Events	
No serious adverse event	0
Prolonged mechanical ventilation (Mechanical ventilation longer than 24 hours during initial postoperative ICU stay)	1
Lung infection (Positive sputum culture in the period between the surgery and when patient meets discharge criteria)	1
Delirium (In the period between the surgery and when patient meets discharge criteria: 1) A DOS score $\geq 3$ at hospital ward AND/OR 2) A positive ICU-CAM score (i.e. feature 1 plus 2 and either 3 or 4 present) at the intensive care by stay $> 1$ day AND/OR 3) Diagnosis confirmed by a psychiatrist, geriatrist or supervising specialist according to the DSM-IV criteria)	1
Re-admissions to intensive care unit (In the period between the surgery and when patient meets discharge criteria)	1
Deep wound infection (deeper tissues are affected (muscle, sternum and mediastinum) and must include: 1) surgical drainage / refixation OR 2) an organism is isolated from culture of mediastina tissue or fluid OR 3) antibiotic treatment, because of sternum wound) (up to 120 days)	2
Re-admissions to hospital (The number of an overnight hospital stay in the period between 30 days after surgery and one year after surgery)	1
Any cardiothoracic surgical interventions (graft- or valve failure, CABG, valve, aortic or other cardiac surgery  )	2
Any percutaneous interventions (PCI, TAVI, etc.)	1
Myocardial infarction (According to the third universal definition of myocardial infarction  )	2
Cerebral vascular accident (CVA)/stroke (Acute neurological event of at least 24 hours of duration, with focal signs and symptoms and without evidence supporting any alternative explanation. Diagnosis of stroke requires confirmation by CT or MRI or pathological confirmation.)	2
Death (all-cause mortality)	3
Total score = sum of physical status en serious adverse events	

According to the definitions of the 'Begeleidingscommissie Hartinterventies Nederland'; Thygesen et al., 2012; ICU: Intensive care unit; CABG: coronary arterial bypass graft; PCI: percutaneous coronary intervention; TAVI: transcatheter aortic valve implantation

Table 3: definitions of the secondary complications and events

Parameter	Definition

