#### 8.2.2 Serious adverse events (SAEs)

A serious adverse event is any untoward medical occurrence or effect that

- results in death;
- is life threatening (at the time of the event);
- requires hospitalisation or prolongation of existing inpatients' hospitalisation;
- results in persistent or significant disability or incapacity;
- is a congenital anomaly or birth defect; or
- any other important medical event that did not result in any of the outcomes listed above due to medical or surgical intervention but could have been based upon appropriate judgement by the investigator.

Events are common among patients who undergo heart surgery (e.g. infections, stroke, and mortality). SAE's that occur during the regular hospitalization phase after the surgery will not be reported to the accredited METC, but will be registered in regular database of the UMCG.

The occurrence of AEs and SAEs are checked and asked at the patient at T2, T3, T4 and T6 by the researcher.

The investigator will report the SAEs through the web portal *ToetsingOnline* to the accredited METC that approved the protocol, within 7 days of first knowledge for SAEs that result in death or are life threatening followed by a period of maximum of 8 days to complete the initial preliminary report. All other SAEs will be reported within a period of maximum 15 days after the investigator has first knowledge of the serious adverse events.

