## 9. STATISTICAL ANALYSIS

### 9.1 Primary study parameter(s)

The primary endpoint is a composite score of functional status, postoperative surgical complications, hospital readmission and MACE. The summary score is calculated for each patient according to Table 2. Missing data on quality of life will be filled with the worst-case score for that component in the analysis. The mean and standard deviation for the summary scores of each group are calculated and handled as a continue variable. Multivariate analyses, inclusive multilevel analyses, are performed to determine time\*group differences at three months and one year after surgery.

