### 9.2 Secondary study parameter(s)

#### *Complications and events*

The incidence of atrial fibrillation, re-thoracotomies, prolonged stay at the intensive care unit and parameters of the primary endpoint are determined. In addition, group differences are tested by chi-square tests. Group difference for re-admissions to hospital and hospitalization days are tested with the Mann-Whitney test, because these variables are usually positively skewed.

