#### *Risks*

No additional risks are expected during the measurements (physical tests). The physical tests can be performed at submaximal aerobic performance and are considered to be safe and feasible in cardiac surgical patients. In standard care a cycling test is performed to ensure patients eligibility to cardiac rehabilitation. This test is performed

before inclusion to the study, patients who are eligible to the CR program are thus able to perform the physical tests performed in this study.

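### Section 9 plans no between-arm summary of recorded AEs and SAEs, so harms before surgery, unlisted admissions before day 30 and non-serious training injuries reach no comparison

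*Combined protocol and SAP*

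**What the plan says.** AEs and SAEs are collected in two ways. Section 8.2.1 is open-ended: "All adverse events reported spontaneously by the subject or observed by the investigator or his staff will be recorded". Section 8.2.2 adds a schedule common to both arms: "The occurrence of AEs and SAEs are checked and asked at the patient at T2, T3, T4 and T6 by the researcher".

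Section 9 makes no use of either record as such. For the primary endpoint, section 9.1 says "The summary score is calculated for each patient according to Table 2". For secondary events, section 9.2 says "The incidence of atrial fibrillation, re-thoracotomies, prolonged stay at the intensive care unit and parameters of the primary endpoint are determined", followed by "In addition, group differences are tested by chi-square tests"; readmissions and hospitalisation days are compared by the Mann-Whitney test. Nothing in sections 9.1 to 9.4 defines a safety summary, a risk period starting at randomisation, or a by-arm AE or SAE table.

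On setting, PRE+POST follows its programme at the UMCG rehabilitation site, whereas "The POST group will receive the CR in the referred hospital" (section 2, Randomization). Section 7.2 says that medical staff and researchers are not blinded. Section 8.5 forgoes a safety board, and section 10.4 judges risk to be minimal. Both argue from the study measurements, not from the two programmes being compared.

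**The concern.** The randomised contrast consists of an added preoperative training phase, an added inpatient phase and a different outpatient phase. A fair account of that contrast needs its harms as well as its benefits, compared from the moment of allocation. The T2 check is the scheduled safety record of the preoperative phase, and no planned result uses it. Followed exactly as written, the trial could declare PRE+POST more effective while an injury, arrhythmia or admission between randomisation and surgery counts in no comparison.

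There is a second, conditional issue. The plan does not say which AE source a later safety table would use. If analysts pooled everything recorded under section 8.2.1, unblinded staff would have had many more occasions to notice minor events in one arm than in the other.

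**Working it through.** **1. Which events are compared, and from when** (section 2, Screening outcomes; Tables 2 and 3; section 7.3, Procedure of primary outcome)

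| Event | Window |
|---|---|
| Lung infection, delirium, ICU readmission, atrial fibrillation | Surgery until discharge criteria are met |
| Prolonged ventilation, prolonged ICU stay | Postoperative hospital stay |
| Deep wound infection, re-thoracotomy | Up to 120 days after surgery |
| Hospital readmission, hospitalisation days | Day 30 to one year after surgery |
| Cardiothoracic and percutaneous interventions | Up to one year; patients are asked about the time since surgery |
| MI, CVA | Up to one year after surgery; start not spelled out |
| Death | Up to five years after surgery; start not spelled out |

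For MI, CVA and death I read the window as starting at surgery, because the endpoint is defined at three months and one year after surgery. If preoperative MI, CVA and death were counted, the remaining preoperative harms would still be outside.

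**2. What is left out**
- Randomisation to surgery: admissions, arrhythmia and injuries. Even atrial fibrillation, a listed event, is not counted before surgery.
- Before day 30: any admission that is not itself another listed event.
- Any time: non-serious AEs such as falls or musculoskeletal injury during training.

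**3. Contact in the uncovered periods** (section 4 and Table 1)
- PRE+POST before surgery: 3 per week × 4 to 6 weeks = 12 to 18 sessions.
- PRE+POST inpatient phase: 15 to 18 days.
- Sum: 12 + 15 = 27 to 18 + 18 = 36 contact days. Taking off two days for the weekend at home gives 25 to 34.
- POST: 0 programme contacts before surgery and 0 in weeks 2-4.

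Section 10.4 gives an average postoperative stay of seven days. The inpatient phase then ends at about day 7 + 15 = 22 to 7 + 18 = 25, before readmissions start to count at day 30.

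**4. Contact over the whole programme**
- PRE+POST: add 2 × 4 = 8 outpatient sessions (section 4 text), giving 35 to 44, or 3 × 4 = 12 (Table 1 heading), giving 39 to 48. The two passages disagree and must be reconciled; the conclusion does not depend on which applies.
- POST, usual: 2 × 6 = 12 sessions. Ratio 35/12 = 2.9 to 48/12 = 4.0.
- POST, prolonged to 8-12 weeks at 2 per week: 16 to 24 sessions. Ratio 35/24 = 1.5 to 48/16 = 3.0.
- POST, extreme of 3 per week for 16 weeks: 48 sessions. Ratio 35/48 = 0.7 to 48/48 = 1.0.

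**5. What pooling could do**

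The plan states no AE or SAE rate, so there is no safety figure to reproduce. The arm size used below does reproduce: 2 × (1.96 + 0.84)² × 0.9² / 0.3² gives 142 per arm, and the t-test version gives 142.2, so 143 as stated.

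Assume the same true incidence in both arms, with only the captured share differing. The recorded ratio is then the PRE+POST share divided by the POST share. The last two columns give the chance that a two-sided 5% test shows an excess in PRE+POST with 143 per arm.

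| Assumed capture, POST vs PRE+POST | Recorded ratio | Recorded % if true incidence is 30% | Chance at 30% | Chance for true incidence 10% to 50% |
|---|---|---|---|---|
| 90% vs 95% | 1.06 | 27.0 vs 28.5 | 5% | 4% to 6% |
| 80% vs 90% | 1.13 | 24.0 vs 27.0 | 8% | 5% to 13% |
| 60% vs 80% | 1.33 | 18.0 vs 24.0 | 24% | 10% to 43% |
| 50% vs 90% | 1.80 | 15.0 vs 27.0 | 70% | 26% to 95% |

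The capture shares and incidences are my assumptions. The documents give neither.

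**The case against.** The strongest reply is that much of the serious harm is already analysed. Table 2 places most of the primary composite under a serious adverse event heading, section 9.2 tests each component separately, and Table 3 counts overnight stays for any reason from day 30. Heart failure, syncope or chest pain leading to an overnight stay after day 30 is therefore compared, and the PRE+POST outpatient phase, which starts at about week 5, lies inside that window. This stands. A reader might infer that AEs and SAEs enter no analysis at all; the documents do not support that.

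A reader might also infer that PRE+POST will look less safe because it is watched more. That goes too far as well. No section proposes pooling or comparing all recorded AEs, the four structured checks follow the same schedule in both arms, and the staff whose observations count are not defined, so programme therapists may not be included. Prolonged POST programmes narrow the overall contact gap and at the extreme close it. They do so only late, however: before surgery and in weeks 2-4 the contrast stays at 27-36 against 0.

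Finally, some oversight exists. SAEs outside the regular postoperative hospital stay go to the ethics committee, SAEs appear in the annual progress report, and the interim rule can stop the trial in either direction. None of these is a planned comparison of recorded AEs and SAEs by arm.

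**Conclusion.** The point holds as an omission with definite limits. Section 9 compares the Table 2 and Table 3 events and nothing else recorded under section 8.2. Three groups of harms fall outside: those between randomisation and surgery, admissions before day 30 that are not another listed event, and non-serious training injuries. The first two fall where programme exposure differs most, about 27-36 contact days against none. This rests on reading the event windows as starting at surgery, which is explicit for most items and implied for MI, CVA and death.

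Unequal ascertainment is a risk for a later pooled table, not a fault in a planned analysis. Its size is unknown; a recorded ratio of about 1.06 to 1.8 is only what the assumed capture shares produce. Nothing in the documents shows that the added phases cause harm. The primary analysis is not invalidated, but the plan should be amended, because as it stands a claim of greater effectiveness could be made without the matching comparison of harms.

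**What to change.** Add to section 9.2 a descriptive safety table for all randomised patients, by allocated arm and from randomisation. Give the number and proportion with at least one SAE and with at least one AE, with risk difference and 95% CI, by period: T1-T2, T2-T3, T3-T4 and T4-T6.

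- **SAEs:** count all, whatever their source, including deaths from the municipal administration and hospitalisations confirmed in records. Include patients who die or leave before a visit. Limiting SAEs to the visit checks would lose deaths and events known only between visits.
- **Non-serious AEs:** base the comparison on the common T2, T3, T4 and T6 checks.
- **Source:** record the source of each AE, and list staff-observed and volunteered AEs separately, without a between-arm test.
- **Definitions:** say who counts as staff in section 8.2.1 and how events at the referred hospitals are captured.

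The cost is a paragraph, one table and a source field on the AE form; the events themselves are already collected. Two drawbacks remain: minor AEs noted only between visits leave the comparison, and checks made by unblinded researchers reduce unequal ascertainment without removing it.

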#### 8.2.2 Serious adverse events (SAEs)

A serious adverse event is any untoward medical occurrence or effect that

- results in death;
- is life threatening (at the time of the event);
- requires hospitalisation or prolongation of existing inpatients' hospitalisation;
- results in persistent or significant disability or incapacity;
- is a congenital anomaly or birth defect; or
- any other important medical event that did not result in any of the outcomes listed above due to medical or surgical intervention but could have been based upon appropriate judgement by the investigator.

Events are common among patients who undergo heart surgery (e.g. infections, stroke, and mortality). SAE's that occur during the regular hospitalization phase after the surgery will not be reported to the accredited METC, but will be registered in regular database of the UMCG.

The occurrence of AEs and SAEs are checked and asked at the patient at T2, T3, T4 and T6 by the researcher.

The investigator will report the SAEs through the web portal *ToetsingOnline* to the accredited METC that approved the protocol, within 7 days of first knowledge for SAEs that result in death or are life threatening followed by a period of maximum of 8 days to complete the initial preliminary report. All other SAEs will be reported within a period of maximum 15 days after the investigator has first knowledge of the serious adverse events.

**8.2.3 Suspected unexpected serious adverse reactions (SUSARs)**

Not applicable

**8.3 Annual safety report**

Not applicable

**8.4 Follow-up of adverse events**

All AEs will be followed until they have abated, or until a stable situation has been reached. Depending on the event, follow up may require additional tests or medical procedures as indicated, and/or referral to the general physician or a medical specialist. SAEs need to be reported till end of study within the Netherlands, as defined in the protocol

**8.5 [Data Safety Monitoring Board (DSMB) / Safety Committee]**

No additional risk is expected during the conduction of the measurements. Patients' eligibility are in routinely care checked with a cycling test. An ongoing safety surveillance was therefore not deemed necessary.

## 9. STATISTICAL ANALYSIS

### 9.1 Primary study parameter(s)

The primary endpoint is a composite score of functional status, postoperative surgical complications, hospital readmission and MACE. The summary score is calculated for each patient according to Table 2. Missing data on quality of life will be filled with the worst-case score for that component in the analysis. The mean and standard deviation for the summary scores of each group are calculated and handled as a continue variable. Multivariate analyses, inclusive multilevel analyses, are performed to determine time\*group differences at three months and one year after surgery.

